The typical approach to the management of GDM is by proper diet and exercise. When blood sugar levels are not maintained within normal levels with diet and exercise, then a medication regimen is necessary. The American College of Obstetrics and Gynecology (ACOG) guidelines suggest that oral medications as well as insulin are suitable for the treatment of GDM. Literature also, suggests that it is not necessary for patients to use insulin for the treatment of GDM prior to the use of oral medications.

Pregnant women are no more or less compliant than other diabetics. It is well documented that the use of oral agents improves compliance and is easier to dose. The failure rate of both glyburide and metformin during pregnancy has been studied. The failure rate of glyburide in pregnancy is 16-20%. The failure rate of metformin in pregnancy is 34-40%. The failure rates of glyburide and metformin have not been studied locally.

Glyburide is an antihyperglycemic agent in the sulfonylurea class. It has been used in pregnancy since 2000 when a landmark paper was published demonstrating the efficacy and safety of its use in pregnancy. Glyburide is FDA pregnancy category B indicating that it may safely be used in pregnancy. Glyburide works by activating the ATP-sensitive potassium channels in pancreatic beta cells which stimulates insulin release. The major side effect associated with glyburide is hypoglycemia. This problem is common to all antihyperglycemic agents and is not unique to glyburide. This effect can be ameliorated with close attention to correct caloric intake. Glyburide should not be used in patients with sulfa allergies.

Metformin is FDA pregnancy category B indicating it is considered safe for use in pregnancy. Metformin is a biguanide antihyperglycemic agent which works by increasing sensitivity to the action of insulin. Metformin

has minimal risk of hypoglycemia. The most common side effect is gastrointestinal upset which usually resolves within one week of medication initiation.

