Glucovance is a drug combination of glyburide and metformin (aka glucophage). Both glyburide and metformin have been studied individually in pregnancy and are often used together in pregnancy as separate doses of each drug. The combined drug, glucovance, has not been studied in pregnancy. Glyburide and metformin have complementing mechanisms of action, so patients who take glucovance may have better glycemic control.

Oral antidiabetic drugs have been found suitable for the management of gestational diabetes because of their ability to provide good glycemic control when used properly. It is known that glyburide and metformin do cross the placenta, but there are no recorded long-term studies that have shown the implications of in utero exposure to these drugs.

[figure not shown]
Current literature notes that glyburide has been associated with higher neonatal birth weight, neonatal hypoglycemia, increased macrosomia (Jiang et al., 2015). No studies indicated increased fetal death associated to the use of oral blood sugar medications. Glyburide and Metformin have been studied extensively for use in pregnancy; however there are no published studies on the use of the combination drug glucovance during pregnancy. The failure rate for metformin and glyburide used as single agents is relatively high. The purpose of this study is to see if the combination drug has a lower failure rate. The proposed study will compare glyburide and glucovance in the treatment of gestational diabetes.

**STUDY DESIGN:** A randomized open label study of patients with GDM not controlled with diet.

Patients will be randomized to either glucovance or glyburide. Sixty-Seven patients are required in each arm.

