The medications, glyburide or glucovance, will be provided to the participants at no cost during the time they are in the study or until they deliver. Medications will be dispensed by any of the UMC Outpatient Pharmacies. Participants will be given information about the pharmacies available and their hours of operations (see patient pharmacy information handout).

The funds to purchase these medications come from the department of OB/GYN, and no funding will be provided by any pharmaceutical company. The Prescriptions will be identified on the prescription with a unique study identifier. During the study duration, monthly reports will be generated to identify those prescriptions pertaining to the study and monthly bills will be generated, for those identified prescriptions. (For details on pricing and dosage please refer to attached email)

Participants who withdrawal from the study or who are no longer taking the study medication (such as other oral medications or insulin), will be responsible for the cost of their medications.

Subjects may have potential side effects or allergy to medication. Each patient will be given a generic information sheet from the pharmacy that indicates the side effects and signs and symptoms of an allergic

reaction to the medication. Also, the potential side effects will be discussed with the patient by the MFM at the time the medications are being prescribed. (See attached information sheet for glucovance and glyburide) Patients will be encouraged to notify PI of any side effects noted while taking the medication. Any side effects reported by the patient or noted through medical records will be documented and reviewed promptly and reported as required to IRB and/or FDA.

Participant medical charts (Texas Tech and UMC) will be reviewed to obtain information on fetal and maternal complications, outcomes, drug dosages, side effects, and gravida and para will be collected for analysis. (See data collection sheets for detailed variable list) Only infant information available in the mother's chart will be abstracted.

Medication Side Effects (per pharmacy patient information sheet, the information sheet may be revised by the pharmacy at any time)

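### Side effects are gathered by patient report and chart note in an open-label trial with no common symptom question described, so any by-arm comparison of stomach upset is at risk of differential reporting

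*Combined protocol and SAP*

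**What the plan says.** The study design statement gives "A randomized open label study of patients with GDM not controlled with diet", so each woman and her physician know which drug she takes.

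On capture, the METHOD section says "Patients will be encouraged to notify PI of any side effects noted while taking the medication" and "Any side effects reported by the patient or noted through medical records will be documented and reviewed promptly". The same section lists side effects among the items taken from the medical charts for analysis, and refers to data collection sheets for the full variable list.

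On briefing, it says "Each patient will be given a generic information sheet from the pharmacy that indicates the side effects", cites sheets for both products ("See attached information sheet for glucovance and glyburide"), and adds that "the potential side effects will be discussed with the patient by the MFM at the time the medications are being prescribed". It also notes that the pharmacy may revise its sheet at any time.

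On what to expect, the BACKGROUND says of metformin: "The most common side effect is gastrointestinal upset which usually resolves within one week of medication initiation". It names hypoglycemia as glyburide's major side effect. It gives no rate for either.

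On outcomes, Specific Aim 2 names hypoglycemia and drug failure. No aim names a gastrointestinal outcome. The Data analysis section says in general terms that outcomes will be compared between groups, and specifies no side-effect analysis.

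**The concern.** Glucovance is glyburide plus metformin, so metformin is the component that separates the arms. Its foreseeable tolerability cost is stomach upset, a symptom that enters the data only if a woman mentions it or someone writes it in the chart. When women know their drug and have been told about that drug's effects, the chance that a given upset is reported may differ between arms. A table of side effects by arm would then mix the effect of the drug with the chance of being recorded.

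The two drugs' main side effects are also treated unequally. Hypoglycemia is a named outcome and has a common procedure: all women are taught the symptoms, measure glucose daily and have their records reviewed. Stomach upset has neither a named outcome nor, in the available text, a common procedure.

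Drug failure is defined in the Sample size calculations section on glucose values alone. Stopping study drug because of stomach upset is therefore not in itself a failure. The METHOD section foresees women who no longer take study medication, but the available text does not say that the reason is recorded. The trial could report fewer failures on glucovance without a dependable account of how well it was tolerated.

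**Working it through.** **1. Common procedure for each side effect**

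| Item | Hypoglycemia | Stomach upset |
|---|---|---|
| Named in an aim | Yes (Aim 2) | No |
| Measured the same way in both arms | Yes: daily glucose values (Glyburide arm, Glucovance arm) | None described |
| Sought by staff | Yes: blood sugar and meal record reviewed (METHOD) | None described |
| Patient report or chart note | Yes | Yes, the only route described |

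**2. The plan's own figure.** The plan has no figure for side effects. The only sample size is 67 per arm for drug failure, 31% v 10%, 80% power, Fleiss formula with continuity correction. With a two-sided alpha of 0.05 (assumed, as none is stated), that formula gives 66, which agrees closely. The point here does not depend on this figure; 67 is used below only as the number of women per arm.

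**3. Effect of unequal capture (assumed inputs).** Let the true rate t be the same in both arms, and let c₁ (glyburide) and c₂ (glucovance) be the fractions of affected women whose upset is recorded.

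Observed RR = (t × c₂) / (t × c₁) = c₂ / c₁, whatever t is.

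- 50% v 70%: 0.70 / 0.50 = 1.4
- 50% v 90%: 0.90 / 0.50 = 1.8

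For the chance of a nominally significant excess on glucovance when the true rates are equal, take p₁ = t·c₁, p₂ = t·c₂, p̄ their mean and n = 67:

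Φ{[(p₂ − p₁) − 1.96 × √(2p̄(1 − p̄)/n)] / √([p₁(1 − p₁) + p₂(1 − p₂)]/n)}

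At t = 20%:
- 50% v 70%: 10% v 14% observed; (0.04 − 1.96 × 0.0561) / 0.0560 = −1.25, giving about 11%.
- 50% v 90%: 10% v 18% observed; (0.08 − 1.96 × 0.0599) / 0.0596 = −0.63, giving about 26%.
- Equal capture: 2.5%.

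| Assumed true rate | 50% v 50% | 50% v 70% | 50% v 90% |
|---|---|---|---|
| 10% | 2.5% | 7% | 15% |
| 20% | 2.5% | 11% | 26% |
| 30% | 2.5% | 14% | 40% |

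**4. Effect of equal under-capture (assumed inputs).** Passive capture can also hide a real effect. If true rates were 10% v 25% and half of events were missed in both arms, the ratio would stay at 2.5 but the difference would fall from 15 to 7.5 points. Power at 67 per arm would fall from about 63% to about 33%.

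**5. Visit spacing.** The METHOD section gives 6 to 26 weeks in the study and about 7 to 12 visits.

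- 7 visits in 6 weeks: 6 / 7 = 0.9 weeks apart on average
- 12 visits in 26 weeks: 26 / 12 = 2.2 weeks
- 7 visits in 26 weeks: 26 / 7 = 3.7 weeks

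An upset that clears within about a week can fall between visits mainly for women enrolled early. These are averages; the documents do not say when the first visit after starting the drug takes place.

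**The case against.** A reader might infer that the side-effect comparison is biased, with stomach upset over-reported on glucovance because the arms are briefed from different lists. The documents do not support that.

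- **The lists cannot be compared.** The information sheets are cited but were not available for review. Whether the glyburide sheet also mentions stomach upset is unknown.
- **There is a shared step.** Consent is obtained before randomisation, so every woman goes through it before knowing her arm. The consent form was not available either, and it may describe both drugs' effects.
- **The direction is open.** Prompting could inflate a difference, missed early symptoms could hide one, and a true metformin effect would look the same as over-reporting.
- **No gastrointestinal comparison is specified.** It is at most implied by collecting side effects for analysis and by the general sentence on comparing outcomes.
- **Reporting is not tied to visits.** Women are encouraged to report any side effect, so long visit gaps do not by themselves mean lost events.
- **A checklist does not blind anyone.** The same unblinded women would answer it, partly from recall.

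All of this stands, and it reduces the point from demonstrated bias to a risk of bias. It does not remove the point. The data collection sheets, also unavailable, might contain a structured side-effect item. However, the METHOD section names the source of the data as patient report and chart notes, and an abstraction sheet would not change that source. A common question makes the asking equal even though expectation remains.

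**Conclusion.** The point holds as a cheap improvement, not as an error that undermines the trial. As described, passive capture in an open-label trial with drug-specific briefing leaves any by-arm comparison of subjective symptoms, chiefly stomach upset, exposed to differential reporting.

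Its size cannot be derived from the documents. The risk ratios of 1.4 and 1.8, and the 11% and 26% chances of a false nominally significant excess, rest wholly on assumed capture fractions, with the chances also assuming a true rate of 20%. They show how the mechanism works and are not estimates for this trial.

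The point does not extend to drug failure, which is defined on glucose values, and applies less to hypoglycemia, which is also sought from glucose records in both arms. The conclusion is limited to the available text: the information sheets, consent form and data collection sheets could not be checked.

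**What to change.** In the METHOD section, add one short question set, worded identically and asked of every woman in both arms at each existing clinic visit, covering the time since the last visit:

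- stomach upset;
- symptoms of low sugar;
- stopping or skipping study drug because of side effects, and why.

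In the Data analysis section, state that stomach upset and stopping for side effects will be reported by randomised arm with a risk difference and 95% CI. Keep spontaneous reports and chart notes for safety reporting. State that open-label expectation remains a limitation, because the common question makes the asking equal but does not blind the answer. If the data collection sheets already hold such an item, cite it in the METHOD section and add only the reporting statement.

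Cost: one short form at visits that already take place, more minor events to record, and two more rows in the results. No change to the visit schedule, treatment or sample size is needed.

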#### Glyburide arm:

- Patients will check and record blood glucose fasting and 1 hour after each meal each day. Patients will also keep a diary of all meals. A copy of their diaries will be kept.
- The starting dose of glyburide may be 1.25mg to 5mg QD or BID depending on the degree of hyperglycemia.
- The dose of glyburide will be increased as needed to a maximum of 20mg /day.
- Antenatal testing will be initiated at 28 weeks
- Patients will receive monthly growth scans
- Participants will be asked to fill out a demographic sheet and emergency contact form during their initial enrollment

#### Glucovance arm:

- Patients will check and record blood glucose fasting and 1 hour after each meal each day. Patients will also keep a diary of all meals. A copy of their diaries will be kept.
- The starting dose of glucovance may be 1.25mg/250mg QD or BID increased to a maximum of 20mg/2000 as needed.
- Patients will receive monthly growth scans
- Antenatal testing will be initiated at 28 weeks.
- Participants will be asked to fill out a demographic sheet and emergency contact form during their initial enrollment

Although subjects will be reminded of the importance of following the procedures indicated in the consent form, there will be subjects who write their blood sugar on paper and some who fail to check according to the protocol, and we expect that this is going to happen frequently. This occurrence will not affect the study nor will it have any risk on the subject. Notes-to-file will be documented when these occur

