Each patient will purchase their own blood monitoring devices, but will be shown how to perform proper self-monitoring of blood sugar at home. Patients are instructed to check their blood sugars following the steps below: (See patient information sheet)

1. Wash your hands with soap and warm water
2. Insert a test strip into your meter.
3. Use your lancing device on the side of your fingertip to get a drop of blood. (Gently squeezing and

- massaging your finger before pricking can increase blood flow)
4. Touch and hold the edge of the test strip to the drop of blood, and wait for the result. (Do not remove the test strip until results appear on display screen).
  5. Your blood glucose level will appear on the meter's display.
  6. Compare your results to the glucose range.
    - a. Fasting= 60-95 mg/dL
    - b. 1 hour AFTER meals= 60-140 mg/dL
  7. Any out of range blood sugar levels (high or low) should be reported to your MFM by calling the OB/Gyn clinic at [contact], or notifying the MFM at the next medical visit.

Subjects will be instructed to take medication as prescribed, and informed on the signs and symptoms of hypoglycemia (see sample GDM information guide). Furthermore, the subjects will be instructed to take a fast acting carbohydrate food (see list of foods) for blood sugars 60 mg/dL or below, and will be encouraged to seek emergency care for persistent blood sugars below 60 mg/dL after treatment with food. If hypoglycemia does occur, the participants will be instructed to call the OB/Gyn clinic and notify MFM at the time of their next appointment. Patient's blood sugar and meal journal/record will be reviewed to identify any persistent high or low blood sugars.

Prenatal care will be performed in the diabetes in pregnancy clinic staffed by a maternal-fetal medicine specialist and by residents in obstetrics and gynecology. Decisions regarding medication changes will be made by the attending maternal-fetal medicine specialist.

Participants will be in the study until they deliver. The estimated length of time in the study is between 6 and 26 weeks depending on gestational age at the time of enrollment. Study participants will be followed up during their normal clinic visits. The frequency of clinic visits will vary depending on the need of every subject, but there will be about 7-12 visits and each will be approximately 1 hour long.

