## **EXCLUSION CRITERIA**

- Inability to consent to the study
- Pre-existing diabetes
- G6PD deficiency
- Serum creatinine >1
- Liver disease
- Allergy to sulfa
- Allergy to glyburide (Patients will be assessed for any past medical history to include allergies to this medication)
- Allergy to metformin (Patients will be assessed for any past medical history to include allergies to this medication)
- Fetal anomalies
- Women who will not monitor their blood glucose

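### The plan says missed glucose checks carry no risk to the woman, although several of its own steps against low glucose work only from a home reading

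*Combined protocol and SAP*

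**What the plan says.** In both arms the schedule is the same: "Patients will check and record blood glucose fasting and 1 hour after each meal each day". The paragraph that closes the Glucovance arm section, worded for subjects generally, then anticipates two departures. Some women will write their values on paper, and there will be "some who fail to check according to the protocol, and we expect that this is going to happen frequently". On both together the plan says: "This occurrence will not affect the study nor will it have any risk on the subject". It offers two responses. One is general: "subjects will be reminded of the importance of following the procedures indicated in the consent form". The other is administrative: "Notes-to-file will be documented when these occur".

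Elsewhere the plan describes the hazard and how it is managed. BACKGROUND states: "The major side effect associated with glyburide is hypoglycemia". It also describes Glucovance as glyburide combined with metformin, so women in both arms take glyburide. METHOD tells women to take a quick carbohydrate for a value of 60 mg/dL or below, and says that they "will be encouraged to seek emergency care for persistent blood sugars below 60 mg/dL after treatment with food". It asks them to report out-of-range values, and it has the clinic review the glucose and meal record for persistent highs or lows. Maternal hypoglycemia is also an outcome under Specific Aim 2, with a hypothesis of similar rates in the two arms.

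**The concern.** The no-risk statement covers two different things. A value written on paper is still a value: the woman has seen it and can act on it. A check that was not made gives her nothing to act on and gives the clinic nothing to review. The plan treats the two alike, and it expects them to be frequent.

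Two things are at stake. The first is oversight of the individual woman. A protocol that declares missed checks free of risk gives nobody a reason to look at them as a safety matter. The second is the hypoglycemia comparison in Aim 2. A woman with few readings has few chances to record a low, so a sparse diary can look like an absence of hypoglycemia. If completeness differs between the arms of this open-label trial, recorded rates can differ or agree for reasons unrelated to the drugs.

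**Working it through.** The plan states no figure on this point: neither an expected rate of low readings nor an expected share of missed checks. The finding therefore rests on setting the passages side by side.

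**Step 1. What the no-risk statement covers.** Its subject refers back to the preceding clause, which names both paper recording and failure to check. The sentence after it uses a plural for the events that get a note-to-file. Missed checks are included.

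**Step 2. Which steps need a reading.**

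| Step in METHOD | Needs a home reading? |
|---|---|
| Quick carbohydrate at 60 mg/dL or below | Yes |
| Emergency care for persistent values below 60 mg/dL after food | Yes |
| Reporting of out-of-range values | Yes |
| Clinic review of the record for persistent lows | Yes |
| Teaching on signs and symptoms | No |
| Call to the clinic if hypoglycemia occurs | No |
| Side effects reported by the woman or found in charts | No |

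Four of the seven steps lose their trigger when the check is not made. Three remain.

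**Step 3. What follows.** Both arms take a drug whose major side effect, on the plan's own account, is low glucose. Removing the trigger for four of the responses cannot be free of risk merely because three others remain. The flat statement conflicts with BACKGROUND and METHOD.

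**Step 4. Illustration of lost detection.** Assumptions, none of them from the plan: three meals a day, so 4 checks a day and 4 × 7 = 28 a week; each check is low with the same probability q; readings are independent. With m checks made, the chance of recording at least one low in a week is 1 − (1 − q)^m. For example, 1 − 0.98^28 = 1 − 0.568 = 0.432, and 1 − 0.98^14 = 1 − 0.754 = 0.246.

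| Assumed q | 28 checks | 14 checks | 7 checks | none |
|---|---|---|---|---|
| 1% | 0.245 | 0.131 | 0.068 | 0 |
| 2% | 0.432 | 0.246 | 0.132 | 0 |
| 5% | 0.762 | 0.512 | 0.302 | 0 |

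The same table bears on Aim 2. Suppose both arms had a true rate of 2% per check, but one arm made all its checks and the other made half. The weekly chance of a recorded low would be 43% against 25%, a gap of 43 − 25 = 18 percentage points with no difference between the drugs. Nothing in the documents says that completeness will differ by arm; the example shows why it should be counted.

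**The case against.** The strongest reply is that home readings are not the only protection. Women are taught the symptoms and told to call the clinic if hypoglycemia occurs, an instruction that does not depend on a number. Side effects are also taken from patient reports and charts, and are to be reviewed promptly and reported as required. BACKGROUND says attention to caloric intake can lessen the effect, and all women receive diet counselling. Care is in a clinic staffed by a maternal-fetal medicine specialist, with about 7 to 12 visits. All of this is correct. It lowers the risk, but it does not support a statement that there is none.

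Four stronger readings are tempting and are not supported.

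- *That missed checks receive no safety review.* The diary review exists, and gaps could be noticed there. What can be said is narrower: the visible text names no follow-up specific to missed checks. Some side-effect text is absent from the version reviewed, and the consent form and information guide are cited but not supplied, so nothing is concluded about their content.
- *That home checks are the main or only safeguard.* The documents do not rank the safeguards.
- *That the exclusion criterion contradicts the no-risk statement.* "Women who will not monitor their blood glucose" concerns unwillingness at entry. It gives no safety reason, and the endpoint's need for glucose values explains it equally well.
- *That the percentages measure harm.* They rest on assumed rates, ignore symptoms, and show only that fewer checks record fewer lows.

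**Conclusion.** The concern holds in a limited form. As applied to missed checks, the no-risk statement is wrong on the plan's own text; as applied to paper recording, it is defensible. The conclusion needs no assumed rate: it rests on glyburide being in both arms, on hypoglycemia being its stated major side effect, and on four of the METHOD steps working from a home reading.

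The size of the clinical risk cannot be derived from the documents. As an indication of detection only, halving the checks takes the weekly chance of a recorded low from 24.5% to 13%, 43% to 25%, or 76% to 51%, at assumed rates of 1%, 2% and 5% per check. Real readings are unlikely to be independent or equally likely to be low at every time of day, so these figures show direction and rough scale.

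No sample size, test or stated figure changes. The plan should still be amended, because the statement concerns safety and describes something that the plan expects often.

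**What to change.** 1. Strike the no-risk half of the sentence as it applies to missed checks, and reconcile the paragraph with the hypoglycemia text in BACKGROUND and the home-reading instructions in METHOD.
2. Treat paper recording and missed checks as separate events. The present wording can stay for paper recording.
3. Bring missed checks to the responsible maternal-fetal medicine physician at the diary review already planned, as well as writing the note-to-file. Any clinical action that follows is for the investigators to set.
4. Report recorded against scheduled checks by arm beside the Aim 2 hypoglycemia results, so that lows that were never measured are not read as an absence of hypoglycemia.

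The cost is a wording amendment and a simple count from diaries that the plan already says will be copied and kept. No extra visit or measurement is needed.
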